2 ANALYSIS SETS

2.1 Definition of analysis sets

2.1.1 All subjects analysis set

This analysis set will comprise all subjects screened for the study and will be used for reporting of disposition and screening failures.

2.1.2 Full analysis set

The full analysis set will be used as the primary population for reporting efficacy and safety data. This comprises all subjects randomised into the study who receive at least one dose of IP and will be analysed according to randomised treatment (modified intent-to-treat [mITT] principle). Any major deviations from randomised treatment will be listed and considered when interpreting the safety data.

2.1.3 Pharmacokinetic analysis set

All subjects who received anifrolumab and who had at least one quantifiable serum PK observation post first dose will be included in the PK analysis dataset. All PK summaries will be based on this analysis set.

2.2 Violations and deviations

Protocol deviations that may greatly impact the completeness, accuracy, and/or reliability of the study data or that may significantly affect a subject's rights, safety, or well-being will be summarised.

The final list of protocol deviations will be finalised and documented prior to unblinding the study data and will be based on deviations as defined in the study Protocol Deviation Specification.

During the blind data review (BDR) meetings, protocol deviations will be classified as important or other depending on the impact of the deviation to the analysis and/or the impact to subjects. Only important protocol deviations will be listed and tabulated in the Clinical Study Report (CSR). All protocol deviations are regularly reviewed per the protocol deviation specification document.

3 PRIMARY AND SECONDARY VARIABLES

The baseline is defined as the last measurement prior to Day 1 dose administration. If the Day 1 value is missing or is invalid, the latest assessment prior to dose administration on Day 1 will serve as baseline. If only dates (not times) are recorded then if an assessment occurs on the same day as Day 1 dose administration, it will be considered to have occurred prior to dose administration.

Baseline OCS dose will be defined as the maximum daily OCS dose taken between Day 1 and Day 7, inclusive. If no OCS are taken by the subject on Day 1 or on or before Day 7, the baseline OCS dose will be 0 mg/day.

If not stated otherwise, change from baseline will be calculated as value at the respective time point minus value at baseline.

MMF at randomisation is defined to be the Day 1 MMF dose. If the Day 1 MMF dose is missing, or no MMF is taken by the subject on Day 1, the MMF dose at randomisation will be defined as the Day 2 MMF dose.

Renal biopsies will be adjudicated, however any changes in WHO or ISN/RPS classification values due to adjudication will only be used for sensitivity analyses to evaluate the relationship between biopsy findings and baseline disease activity or response to therapy. For all other analyses and summaries, the local classification of WHO or ISN/RPS will be used.

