7.7.3.2 Corticosteroids

Initial corticosteroid treatment to control LN and SLE:

Subjects may enter the study taking daily OCS at a maximum dose of 0.5 mg/kg/day of prednisone-equivalent not to exceed 40 mg/day. In addition, subjects will receive IV (or oral, if applicable) methylprednisolone pulse 500 mg on the day of randomisation, prior to receiving the IP, unless they received a methylprednisolone pulse of ≥ 500 mg within 10 days prior to randomisation. Subjects may also receive one additional (optional) dose of IV (or oral, if applicable) methylprednisolone pulse (≤ 500 mg) for renal or extra-renal disease activity after the Week 0 (Day 1) visit up to and including the Week 8 visit. Methylprednisolone pulse can be divided and administered on two consecutive days but the cumulative dose must not exceed 500 mg.

Steroid tapering during the 52 week double-blind treatment period:

Oral corticosteroid dose tapering is required during the study with the goal of tapering OCS to prednisone-equivalent of ≤ 10 mg/day by Week 12 and prednisone-equivalent of ≤ 7.5 mg/day by Week 24. The rate of tapering is at the discretion of the Investigator; a recommended tapering schedule is provided in [Appendix O](#). If subjects experience an increase in SLE disease activity upon tapering of OCS their dose may be returned to a dose equal or less as the dose prior to the taper. The return to the pre-taper dose will not be considered an OCS "burst and taper". The pre-taper dose for various periods is defined as follows:

- Week 0 to Week 12: dose at randomisation
- After Week 12 to Week 24: the Week 12 dose
- After Week 24 to Week 40: the Week 24 dose

Subjects unable to taper OCS to ≤ 15 mg/day at Week 12 or < 15 mg/day at Week 24 will be discontinued from IP treatment. However, subjects who exceed the maximum daily OCS dose at the Week 12 or Week 24 visits may continue to receive IP if the current dose is part of a protocol-allowed temporary OCS dose (eg, burst and taper) increase. Subjects who cannot be returned to their pre-increase dose within 14 days from the start of burst will have their IP discontinued at the next visit.

The subjects discontinued from IP treatment will be followed until Week 52 (or for a minimum of 12 weeks after last dose of IP for subjects for whom IP was discontinued within 12 weeks prior to Week 52).

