Investigators will not be required, but may continue, to taper OCS dose beyond the target of 7.5 mg/day up to Week 40. Steroid tapering will not be permitted from Week 40 to Week 52.

Steroid “burst and taper”

A steroid burst is defined as one of the following:

Oral corticosteroid increase up to a maximum daily dose of 0.5 mg/kg/day (maximum 40 mg/day) prednisone-equivalent dose for up to a total of 14 days and that must be fully administered and tapered to less than or equal to the pre-burst starting dose by the end of the 14th day. Any course of OCS burst must not extend beyond Week 40 during the first year (starting after Week 0) and Week 92 during the second year extension period (starting after Week 52), regardless of when the course was started.

OR

A maximum of 1 instance of intra-articular, tendon sheath or bursal injections (for a total methylprednisolone \leq 80 mg or equivalent) can be given. Subjects who receive any intra-articular/tendon sheath/bursal injections should not receive OCS burst (and vice versa).

Steroid burst is allowed as follows:

- **From randomisation to Week 40:** One burst and taper of corticosteroids for increased SLE disease activity or for non-SLE activity is allowed.

Subjects who receive more than one steroid “burst and taper” or who violate the above criterion may continue to receive IP after approval by Sponsor/Designee Medical Monitor, but will be considered non-responders for subsequent responder analyses (such as CRR), regardless of whether the OCS “burst” was administered for increased SLE activity or non-SLE causes.

- **Increase in corticosteroids from Week 40 to Week 52:** No increase in OCS, or the use of IV or intra-articular, tendon sheath or bursal injections is allowed from Week 40 until Week 52 assessment.

Corticosteroid dose from Week 52 to Week 100

- If the OCS dose is >7.5 mg/day at Week 52, tapering to ≤ 7.5 mg/day is required by Week 60. Failure to achieve ≤ 7.5 mg/day by Week 60 will lead to discontinuation from IP.
- OCS dose must be tapered to ≤ 5 mg/day at Week 80. OCS tapering below 5 mg/day is allowed at any time until Week 92.
- No change in OCS dose will be allowed from Week 92 to Week 104.
- One burst and taper will be allowed between Week 52 and Week 92.

Increase in corticosteroids for the prevention of adrenal insufficiency

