3.3.7 Sustained reduction of oral corticosteroid dose

The effect of anifrolumab compared with placebo on the ability to reduce the OCS dose will be assessed in subjects with baseline OCS ≥ 20 mg/day prednisone-equivalent. Sustained reduction of OCS dose is assessed using the difference in proportions of subjects meeting all the following criteria:

- Achieve an OCS dose of ≤ 7.5 mg/day prednisone-equivalent by Week 24
- Maintain an OCS dose ≤ 7.5 mg/day prednisone-equivalent from Week 24 to Week 52
- No discontinuation of IP or use of restricted medication beyond the protocol-allowed threshold before assessment. Allowed restricted medications are defined in [Appendix A](#) and [Appendix B](#).

The proportion of subjects achieving OCS tapering requirement will also be assessed at Week 104:

- Achieve an OCS dose ≤ 5.0 mg/day prednisone-equivalent by Week 80
- Maintain an OCS dose ≤ 5.0 mg/day prednisone-equivalent from Week 80 to Week 104
- No discontinuation of IP or use of restricted medication beyond the protocol allowed threshold before assessment. Allowed restricted medications are defined in [Appendix A](#) and [Appendix B](#).

The standardised area under the curve (AUC) of OCS dose up to Week 52, up to Week 104, and from Week 52 to Week 104 will be calculated as follows:

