4.2.3.3 Oral corticosteroid management

The exploratory endpoint used to evaluate the effect of the anifrolumab regimens versus placebo on the ability to achieve a sustained reduction of OCS dose is the difference in proportions of subjects able to taper OCS to ≤ 7.5 mg/day prednisone-equivalent by Week 24 and maintain this dose through Week 52. The effect of the anifrolumab regimens versus placebo will also be evaluated on the ability to achieve a sustained reduction of OCS dose using the difference in proportions of subjects able to taper OCS to ≤ 5.0 mg/day prednisone-equivalent by Week 80 and maintain this dose through Week 104.

The same CMH approach as described in Section 4.2.2 will be used to estimate the treatment differences between the anifrolumab regimens and placebo at Week 52 and at Week 104. Any missing data will be imputed as defined in Section 4.1.4.

Subgroup analyses will be performed as described in Section 4.3.

Reduction of OCS dose will also be assessed at Week 24 by examining the proportions of subjects able to taper OCS to ≤ 7.5 mg/day prednisone-equivalent by Week 24, using the same analysis approach. Reduction of OCS dose will also be assessed at Week 80 by examining the proportions of subjects able to taper OCS to ≤ 5.0 mg/day prednisone-equivalent by Week 80, using the same analysis approach.

In order to examine the impact of missing data, a tipping point analysis as described in Section 4.2.2 will also be performed for the sustained reduction of OCS dose at Week 52 and Week 104. The analysis for each treatment group, and the pooled anifrolumab group, will only be statistically interpreted if the nominal p-value from the main analysis of sustained reduction of OCS dose detailed above, for the respective comparison with placebo at the specified visit, is <0.05 (in favour of anifrolumab).

Daily OCS doses and changes from baseline will be presented by descriptive statistics by visit for all subjects.

Additionally, the daily OCS dose will be displayed graphically by a longitudinal plot presenting the means and corresponding SDs. The number of subjects will also be included in the graph.

Shift plots (scatter plot) for the daily OCS dose presenting baseline values versus Week 24 values, baseline values versus Week 52 values and Week 52 values versus Week 104 values will also be provided. A diagonal line indicating no change will be included in this shift plot.

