6 CHANGES OF ANALYSIS FROM PROTOCOL

A possible interim analysis for futility may be performed, following results from a pivotal Phase 3 SLE study for anifrolumab in subjects with SLE. In the case that there is sufficient evidence to suggest that anifrolumab in addition to SOC is not beneficial over placebo in addition to SOC for subjects with SLE, consideration can be giving for stopping this study early for ethical reasons. The presence of such evidence can be evaluated only after obtaining results from the second anifrolumab pivotal study in SLE.

The threshold for the analysis of sustained reduction in OCS has been updated from 10 to 20.

The OCS at baseline subgroup categories are changed from (≤ 20 mg/day, > 20 mg/day) in the protocol to (< 20 mg/day, ≥ 20 mg/day) in the SAP for consistency with the sustained reduction in OCS endpoint definition.

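### Baseline OCS is the highest daily dose on Days 1–7, so a permitted early burst can move a low-dose entrant into the ≥20 mg/day population

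*SAP*

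**What the plan says.** SAP section 3 opens with a general rule: "The baseline is defined as the last measurement prior to Day 1 dose administration". Protocol section 8.4 has the same rule and makes no exception for OCS. The next SAP paragraph then sets a different rule for steroids: "Baseline OCS dose will be defined as the maximum daily OCS dose taken between Day 1 and Day 7, inclusive". If no OCS is taken in that week, baseline is 0.

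This variable has several uses:

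- SAP 3.3.7: the ability to reduce OCS "will be assessed in subjects with baseline OCS" of at least 20 mg/day prednisone-equivalent. "Sustained reduction of OCS dose is assessed using the difference in proportions of subjects meeting all the following criteria": a dose of 7.5 mg/day or less by Week 24, that level held to Week 52, and neither IP discontinuation nor disallowed medication.
- SAP 4.3: the <20 versus ≥20 mg/day subgroup, applied to 24-hour UPCR and CRR at Weeks 24, 52 and 104.
- SAP 4.2.3.3: "Daily OCS doses and changes from baseline will be presented by descriptive statistics by visit for all subjects", and shift plots from baseline.

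On permitted steroid use, protocol 7.7.3.2 says of the period from randomisation to Week 40: "One burst and taper of corticosteroids for increased SLE disease activity or for non-SLE activity is allowed". It also provides that "subjects will receive IV (or oral, if applicable) methylprednisolone pulse 500 mg on the day of randomisation", before IP, unless a pulse was given in the preceding 10 days.

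SAP section 6 lists a related change ("The threshold for the analysis of sustained reduction in OCS has been updated from 10 to 20") and the matching subgroup cut, but not the new baseline window. The amendment history for SAP version 4.0 records that the OCS baseline definition was updated and gives no reason.

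**The concern.** A baseline should describe the subject before treatment can act. Here the qualifying dose may be one given after randomisation and after the first infusion, in response to disease activity or an unrelated illness. Two things follow.

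First, the ≥20 mg/day restriction is there so that the sustained-reduction endpoint is measured in subjects with a substantial dose to taper. A subject who entered on a low dose and had a short early burst passes the restriction with nothing to taper. The success criterion is an absolute level, with no required fall from entry, so going back to the entry dose satisfies the dose part of it.

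Second, the OCS subgroup is meant to show whether the effects on 24-hour UPCR and CRR are uniform across entry steroid need. With this definition, membership depends partly on what happened in the first week on study. The change-from-baseline summaries and shift plots have the same problem.

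**Working it through.** The documents give no figure for this point, so there is none to reproduce. The check is one of definitions, with two small calculations.

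**1. Where the window falls.** SAP 4.1.1 counts study days from the first IP administration, which is Day 1. Days 2–7 therefore lie wholly after first dosing.

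**2. Can a permitted burst reach the cut?** Inputs: burst ceiling 0.5 mg/kg/day, capped at 40 mg/day, for up to 14 days, starting after Week 0 (protocol 7.7.3.2); minimum weight 40 kg (inclusion criterion 5); cut 20 mg/day (SAP 3.3.7).

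Ceiling = min(0.5 × weight, 40):

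| Weight (kg) | Burst ceiling (mg/day) |
|---|---|
| 40 | 20 |
| 50 | 25 |
| 60 | 30 |
| 80 or more | 40 |

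A full-dose burst on Days 2–7 meets the cut at every eligible weight.

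**3. One subject traced through both rules.** Assume 60 kg, entry dose 5 mg/day, a full burst starting on Day 4, and return to 5 mg/day within 14 days.

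- Pre-dose rule: baseline 5 mg/day, outside the ≥20 population.
- SAP rule: max(5, 30) = 30 mg/day, inside it.
- From then on 5 ≤ 7.5, so the dose criteria are met if 5 mg/day is held to Week 52. The subject is a responder if IP continues and no disallowed medication is used.
- Recorded fall from baseline: 30 − 5 = 25 mg/day. Fall from entry: 5 − 5 = 0.

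**4. Effect on the comparison (illustration).** Let a share f of the ≥20 population be misclassified, with the same success rate q in each arm. Then observed rate = (1 − f)p + fq, and the difference becomes (1 − f)(p_A − p_P). The values p_A = 50%, p_P = 35% and q = 70–95% are assumptions.

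| f | Anifrolumab | Placebo | Difference (points) |
|---|---|---|---|
| 0 | 50.0% | 35.0% | 15.0 |
| 10% | 52.0–54.5% | 38.5–41.0% | 13.5 |
| 20% | 54.0–59.0% | 42.0–47.0% | 12.0 |
| 30% | 56.0–63.5% | 45.5–53.0% | 10.5 |

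**5. The oral pulse (conditional).** If an oral pulse counted as OCS, 500 mg would be 500/20 = 25 times the cut. Split evenly over two days it would be 250/20 = 12.5 times, before any conversion to prednisone. Nothing in the available text settles whether it counts.

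**The case against.** The best defence is that a short window after the Day 1 pulse is a reasonable way to capture the starting daily dose, since induction OCS may be settled a few days after randomisation. Background treatment already has its own conventions: the same section takes MMF at randomisation from Day 1, or Day 2 if Day 1 has none. This is fair as a motive, but it does not explain the choice of the maximum or the absence of any exclusion for burst doses. Protocol 7.7.3.2 itself uses the randomisation dose as the reference for Weeks 0–12.

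A reader might go further and infer that an oral Day 1 pulse sets baseline at hundreds of mg and swamps the OCS means. The documents do not support that. Exclusion criterion 13 and protocol sections 7.7.2.1, 7.7.2.2 and 7.7.3.2 treat pulses separately from daily OCS. The missing-data sections (protocol 8.5, SAP 4.1.4) describe the Day 1 dose as intravenous. SAP Appendices A to C, which hold steroid rules, are not in the text available for this review. The pulse is also given before IP. What stands is an ambiguity that the baseline sentence should close.

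Nor is success near-certain for a misclassified subject. The level must be held to Week 52 on IP, and the early burst uses up the single one allowed to Week 40.

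**Conclusion.** The concern holds through the burst route, which depends only on text in the two documents. The Days 1–7 maximum departs from the plan's own pre-dose rule. It lets post-randomisation steroid use decide who is in the ≥20 mg/day population and subgroup, and it can count a subject as a sustained reducer with no fall from entry dose.

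The size is unknown, because neither document says how many subjects had a burst in the first week. The shrinkage in the working applies only under its assumed rates and misclassified shares. Because the rule is the same in all blinded arms, inflated response rates and dilution are the expected result. A reader might infer a bias towards anifrolumab, but that would need early bursts to differ by arm within seven days, and nothing in the documents suggests it.

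The reach is limited to an exploratory endpoint, the OCS subgroup analyses and descriptive OCS summaries. The main tests of 24-hour UPCR and CRR do not use this variable. It is a cheap correction worth making, not a threat to the trial's main conclusions.

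**What to change.** Define baseline OCS as the daily prednisone-equivalent OCS dose in effect at the first IP dose, and state that methylprednisolone pulses by any route and burst-and-taper doses do not count. If no such dose is recorded on Day 1, use the first daily dose on or before Day 7 that is neither pulse nor burst; otherwise use 0. A plain Day 2 fallback would not be enough, because a pulse may be split over two consecutive days.

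Apply the definition to the sustained-reduction population, the OCS subgroup, the change-from-baseline summaries and the shift plots. List the change in SAP section 6. Keep the Days 1–7 maximum as a sensitivity analysis for the endpoint and the subgroup.

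The cost is a short SAP edit and one reprogrammed flag. In the few subjects with no Day 1 dose, someone must judge, while still blinded, whether a dose first taken later in the week is a late-started daily dose or a burst.

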3.1 Primary outcome variable

The primary endpoint used to evaluate the effect of anifrolumab compared with placebo on LN disease activity is the relative difference in change from baseline to Week 52 in the 24-hour UPCR.

The time to 24-hour UPCR ≤ 0.7 mg/mg will be analysed as a supportive analysis and will be derived for subjects with baseline 24-hour UPCR > 0.7 mg/mg as the date of first 24-hour UPCR ≤ 0.7 mg/mg minus the date of first dose of IP. If the subject did not achieve 24-hour UPCR ≤ 0.7 mg/mg, the time to 24-hour UPCR ≤ 0.7 mg/mg will be censored at the earliest of the following:

- Date of withdrawal from the study;

- Discontinuation of IP in case of premature discontinuation of IP where the last IP dose is not in the Week 48 analysis visit window;
- Date of the Week 52 observation used in analysis (or the date of the last observation before Week 52 if the Week 52 observation is missing) in case of premature discontinuation of IP where the last IP dose is in the Week 48 analysis visit window;
- Date of the Week 104 observation used in analysis (or the date of the last observation before Week 104 if the Week 104 observation is missing);
- Database extract date.

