1.2.5 Discontinuation of IP

Criteria for discontinuing IP for worsening of LN or SLE (at any time):

Blinded IP will be discontinued in subjects who meet pre-defined criteria for worsening LN or SLE. Subjects may receive rescue treatment as clinically indicated. Subjects who had their IP discontinued will be followed according to the study schedule and should have a 24-hour UPCR measurement within 4 weeks of the decision to discontinue IP and before the start of a new treatment for LN. These subjects will be followed until Week 52 (or for a minimum of 12 weeks after last dose of IP for subjects for whom IP was discontinued within 12 weeks prior to Week 52). If discontinuation occurs during the second year extension period, subjects will be followed until Week 104 (or for a minimum of 12 weeks after last dose of IP for subjects for whom IP was discontinued within 12 weeks prior to Week 104).

- >30% decrease in eGFR compared to baseline due to LN **and** eGFR <60 mL/min/1.73 m² (on two independent samples) **or**
- Increase in renal or extra renal lupus activity requiring prohibited systemic immunosuppressive treatment (e.g. cyclophosphamide, rituximab, belimumab)
- Receipt of >1 methylprednisolone pulse after the day of randomisation
- Receipt of any methylprednisolone pulse after Week 8
- The IP will be discontinued if MMF is discontinued and another immunosuppressant is initiated

Criteria for discontinuation of IP for worsening of LN or SLE at Week 12 and Week 24:

- eGFR <75% of baseline and <60 mL/min/1.73 m² (on two independent samples) **or**
- Nephrotic range UPCR (confirmed by a second measurement at least two weeks after the first measurement):

- Subjects with 24-hour UPCR ≤ 3 mg/mg at baseline will be withdrawn if 24-hour UPCR increases by $>50\%$ from baseline to >3.5 mg/mg
- Subjects with 24-hour UPCR >3 mg/mg at baseline will be withdrawn if 24-hour UPCR at Week 24 >3.5 mg/mg and there is $<60\%$ improvement from baseline **or**
- Inability to adhere to corticosteroids requirements:
 - Inability to reduce OCS to ≤ 15 mg/day prednisone-equivalent at Week 12
 - Inability to reduce OCS to <15 mg/day by Week 24

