The time to first onset of herpes zoster during treatment will be derived as date of first onset of herpes zoster – date of first administration of IP + 1. AEs with an onset date before the date of first administration of IP and AEs with an onset after 28 days after the date of last administration of IP will not be considered for the time to first onset of herpes zoster during treatment. If a subject has no herpes zoster during treatment, the time to first onset will be censored at the date of last administration of IP + 28 days.

For herpes zoster, an alternative event rate per 100 subject years will be derived as the number of subjects with herpes zoster divided by the sum of time at risk in days for all subjects in the analysis set multiplied by 365.25 days/year multiplied by 100. The time at risk is defined as time (including start and end date) from start of period (e.g. date of first administration of IP for events during treatment) to the date of first event, discontinuation or completion of the

study, or the database extract date, whatever comes first. This alternative event rate may also be calculated for other AESIs if suggested by data. This will be discussed during the BDR meeting and the decision will be made before unblinding the data.

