4.2 Analysis methods

4.2.1 Analysis of the primary variable

The primary estimand is evaluating the efficacy on disease activity of the pooled anifrolumab groups relative to placebo in subjects with active proliferative LN. This is measured by the

relative difference in change from baseline to Week 52 in the 24-hour UPCR. The full analysis set (as defined in Section 2.1.2) will be used, and any data collected after IP discontinuation will be excluded from the analysis, in order to reflect the effect of the initially assigned and dosed IP (anifrolumab or placebo), prior to the occurrence of the intercurrent event of IP discontinuation, applying a “while on treatment” estimand strategy. The individual anifrolumab regimens will also be assessed but not as part of the primary analysis.

The estimand for all continuous endpoints (including the primary endpoint) follows the “while on treatment” strategy, which includes data only up to IP discontinuation. If IP has not been reported as prematurely discontinued, available data up to and including Week 104 will be used for continuous endpoints analyses. Otherwise, the date of IP discontinuation will be determined as the date of last IP administration. However, all subjects who have an infusion of IP within the Week 48 analysis visit window will be determined to have completed treatment in the double-blind treatment period, and their Week 52 data will be included in the analyses.

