- Biopsy analysis: Excludes any subjects whose adjudicated kidney biopsy results show them to be ineligible for study entry (i.e. subjects whose adjudicated kidney biopsy results are not class III or class IV)

Subgroup analyses will be performed as described in Section 4.3.

Summary statistics for 24-hour UPCR and change from baseline will be presented by week. Longitudinal presentations of results over time (i.e. for each post-baseline visit up to Week 104 where 24-hour UPCR is recorded) based on the same main analysis, with the corresponding 95% CI, will be created. Mean changes from baseline for 24-hour UPCR will be displayed in a longitudinal plot by treatment group only for the first year, where the estimated adjusted means with corresponding 95% CI at each visit will be displayed. A Kaplan-Meier plot will also be produced for time to 24-hour UPCR ≤ 0.7 mg/mg by treatment group for the whole study.

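### Time to 24-hour UPCR ≤0.7 (SAP 3.1): the IP-stop cut-off applies to non-responders but not to events, so the Kaplan-Meier curve is biased upward whenever subjects respond after stopping IP

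*SAP*

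**What the plan says.** SAP 3.1 defines a supportive variable for subjects with baseline 24-hour UPCR above 0.7 mg/mg. The time is the "date of first 24-hour UPCR ≤ 0.7 mg/mg minus the date of first dose of IP". The censoring list opens with a condition: "If the subject did not achieve 24-hour UPCR ≤ 0.7 mg/mg, the time to 24-hour UPCR ≤ 0.7 mg/mg will be censored". Several candidate dates follow, and whichever comes first applies. One of them is "Discontinuation of IP in case of premature discontinuation of IP where the last IP dose is not in the Week 48 analysis visit window". No sentence says that a response must occur before that date to count.

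SAP 4.2.1 specifies the output: "A Kaplan-Meier plot will also be produced for time to 24-hour UPCR". That plot uses the same ≤0.7 threshold, is split by arm and covers both study years. The same section says, in its text on continuous endpoints, that "the date of IP discontinuation will be determined as the date of last IP administration" once premature discontinuation is reported.

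Post-stop values will exist. SAP 1.2.5 states: "Subjects who had their IP discontinued will be followed according to the study schedule and should have a 24-hour UPCR measurement within 4 weeks". Those four weeks run from when stopping is decided. It adds: "Subjects may receive rescue treatment as clinically indicated". Protocol 4.2.2 lists the 24-hour urine among the minimum assessments for subjects who have stopped IP, and Protocol 5.1 schedules it at Weeks 12, 24, 36, 52, 64, 76, 88 and 104.

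**The concern.** Kaplan-Meier requires that leaving the risk set at a given time does not depend on what happens to that subject afterwards. Here it does. Take two subjects who both stop IP at Week 14 without having responded. One reaches UPCR ≤0.7 at Week 52 and, under the literal rule, is at risk throughout and is an event at Week 52. The other never reaches it and is removed at Week 14. The post-stop failures are dropped from the denominator and the post-stop successes are kept.

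The curve then matches neither sensible target. It is not an on-IP curve, because it credits responses after IP, some possibly on rescue. It is not a treatment-policy curve, because stoppers who fail are not followed. It is the time-to-event display attached to the primary variable, so readers will set it beside the primary result.

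**Working it through.** **The plan's own figures.** The documents give no figure for this curve, no IP-stop rate and no post-stop response rate. The nearest stated figure is the power of about 87% in SAP 1.3. It reproduces: SE = 0.8 × √(1/50 + 1/100) = 0.1386; |ln(0.35/0.54)| = 0.4336; 0.4336/0.1386 − 1.961 = 1.168, which gives 87.9%. It does not depend on this variable.

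**Hand check (assumed counts).** Of 100 subjects, 20 stop IP at Week 14 without a response. At Week 52, 8 of those 20 and 32 of the 80 stayers are at ≤0.7.

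- As written: the 12 non-responding stoppers are censored at Week 14, so 88 are at risk at Week 52 with 32 + 8 = 40 events. 40/88 = 45.5%.
- Events bounded at IP stop as well: 32/80 = 40%.
- Everyone followed regardless of IP: 40/100 = 40%.

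**General form.** For a single response visit, let s be the share who stop beforehand without a response, p the response among stayers and q the response among stoppers. As written, the estimate is [(1 − s)p + sq] / [(1 − s) + sq]; with events bounded it is p. The difference is sq(1 − p) / (1 − s + sq). With s = 0.2 and p = q = 0.4 this is 0.048/0.88 = 5.5 points, as above. It is zero when q = 0, and it rises with both s and q.

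**Simulation (400,000 subjects per scenario).** UPCR at Weeks 12, 24, 36 and 52. Assumed: on-IP response 15% per visit, and stopping spread evenly over Weeks 8 to 44, independent of response. Without stopping, the Week 52 response is 1 − 0.85⁴ = 47.8%.

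Post-stop response equal to on-IP response (15% per visit):

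| Stop share | As written | Events bounded at IP stop | All followed | As written − bounded |
|---|---|---|---|---|
| 10% | 49.5% | 47.8% | 47.8% | +1.7 |
| 20% | 51.4% | 47.8% | 47.8% | +3.6 |
| 30% | 53.6% | 47.9% | 47.9% | +5.7 |
| 40% | 56.2% | 47.9% | 47.9% | +8.3 |

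Post-stop response varied (as written − bounded, in points):

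| Post-stop response per visit | 20% stop | 40% stop |
|---|---|---|
| 0% | 0.0 | 0.0 |
| 5% | +1.3 | +3.4 |
| 10% | +2.6 | +6.1 |
| 15% | +3.6 | +8.3 |
| 25% | +5.3 | +11.9 |

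Twenty per cent stopping with 15% post-stop response (+3.6) is about the same as 40% stopping with 5% (+3.4). The stop rate alone does not fix the size.

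**The case against.** The best reply is that the SAP already removes post-stop data. SAP 4.1.3 and 4.2.1 restrict continuous endpoints, including the primary one, to data up to IP discontinuation. The plot is specified in 4.2.1, the variable comes from the same UPCR values, and the censoring list mirrors the 4.2.1 rule, including its Week 48 window exception. If that restriction governs this variable, no post-stop response enters and the event and censoring rules agree.

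This has weight, and a reader who infers that post-stop responses will certainly be counted goes beyond the text. But it does not close the gap:

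- The restriction is worded for continuous endpoints, and this is a time-to-event variable.
- The SAP 5.0 amendment history lists the while-on-treatment clarification and the revised time-to-event censoring as separate items, and the second mentions only censoring dates.
- Post-stop UPCR stays in the data for the treatment-policy sensitivity analysis in 4.2.1, so a programmer working from 3.1 would find it.
- Where the SAP wants events bounded, it says so. For herpes zoster (SAP 3.6.1), "AEs with an onset after 28 days after the date of last administration of IP will not be considered". For time to CRR (SAP 3.2.1), no discontinuation of IP is part of the response itself. The herpes zoster contrast is only suggestive, since a rule for continuous endpoints would not reach adverse events.

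Two further points stand. Exposure is limited: subjects who finish first-year dosing and do not enter the extension have only spot UPCR at Weeks 56 and 60 (Protocol Table 3), so the problem concerns those who stop before the Week 48 window or during the extension. And no test is planned on this curve; the hierarchy in SAP 4.1.2 covers only 24-hour UPCR and CRR.

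**Conclusion.** The point holds as a defect in the written rule. SAP 3.1 bounds censoring at IP stop and leaves the event unbounded. Followed literally, it biases the curve upward whenever stoppers respond after stopping; at best, two programmers could draw different curves from the same text.

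The 2 to 8 points rest on assumed rates (15% response per visit on and off IP, 10% to 40% stopping), so they illustrate the size and do not predict it.

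A reader might infer that the curve is inflated most in the arm with most stopping, that this arm is placebo, and that the gap between arms is therefore understated. The documents do not support this. They give no stop rates by arm, and the bias also depends on post-stop response, which could differ between arms. The direction of any distortion of the comparison is unknown. Nor does anything here touch the primary MMRM, CRR, alpha or power. It should be corrected, but it is not critical.

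**What to change.** In SAP 3.1, compute the cut-off (the earliest of the listed dates) for every subject. Count an event only if the first 24-hour UPCR ≤0.7 falls on or before it; otherwise censor at the cut-off. State there which date stands for IP discontinuation, since 4.2.1 defines it only in its text on continuous endpoints. This matches the while-on-treatment estimand.

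The downside should be noted beside the plot: censoring everyone at IP stop still assumes that stopping is unrelated to prognosis, which is doubtful because IP is stopped for worsening LN (SAP 1.2.5). A version treating IP stop as a competing event would show how much this matters.

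The alternative is to remove the IP-stop cut-off for all subjects, follow everyone, and label the curve treatment-policy. That avoids the assumption but includes responses on rescue.

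Either change costs one sentence and a small programming edit, needs no new data, and should be made before unblinding.
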